8.0 Handling of Potential Intercurrent Events for the Primary and Secondary Endpoints

The primary and secondary endpoints (Section 3.1 and Section 3.2) will be analyzed in the ITT Population and no intercurrent events will impact the analysis. All data collected, regardless of premature discontinuation of study drug, will be used in the analysis.

9.0 Efficacy Analyses

9.1 General Considerations

All efficacy analyses will be conducted in the ITT Population.

The only and final analysis for the primary and secondary efficacy endpoints as well as all other efficacy endpoints will be performed after the last on-going subject completes the follow-up phone call or withdraws from the study and the database has been locked.

Descriptive summary statistics will be provided for efficacy endpoints at each visit by treatment groups based on the ITT population. There will be no statistical testing.

Categorical efficacy endpoints at each visit will be summarized by number of subjects, the number and percentage of subjects who achieve the endpoint, as well as the 95% confidence interval (CI) based on normal approximation.

Continuous efficacy endpoints at each visit and change from baseline at each visit will be summarized by descriptive summary statistics including number of subjects, mean, standard deviation, median, minimum, maximum. The 95% CI based on normal approximation will be provided for the mean change from baseline.

"Baseline" refers to the last non-missing observation before the first administration of study drug or randomization if no study drug is given.

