2.0 Study Design and Objectives

2.1 Objectives, Hypotheses and Estimands

The primary objective of this study is to assess the safety and efficacy of cedirogant versus placebo for the treatment of moderate to severe plaque psoriasis in adult subjects who are candidates for systemic therapy or phototherapy.

The primary objective of the study is to demonstrate a higher rate of subjects achieving Psoriasis Area and Severity Index (PASI) 75 (defined as $\geq 75\%$ reduction from Baseline in PASI) at Week 16 with at least one cedirogant dosing group compared to placebo in the Intent-to-Treat (ITT) population, which consists of all randomized subjects.

The primary endpoint is the achievement of PASI 75 at Week 16.

The secondary efficacy objective of the study is to demonstrate a higher rate of subjects achieving static Physicians Global Assessment (sPGA) score of clear or almost clear,

PASI 50/90/100, Psoriasis Symptoms Scale (PSS) total score of 0 for subjects with PSS>0 at Baseline, and itch Numerical Rating Scale (NRS)≥4-point improvement from Baseline for subjects with itch NRS≥4 at Baseline, at Week 16 with cedirogant compared to placebo in the ITT population.

As the study was terminated prematurely before the planned number of subjects could be randomized, all efficacy data will be summarized using descriptive summary statistics without statistical comparison or statistical testing. No hypotheses or estimands are defined for the primary and secondary efficacy endpoints.

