2.4 Sample Size Determination

Given the planned total sample size of 200 subjects (50 subjects in each arm), the study has more than 95% power to detect the treatment differences of 60% in PASI 75 in at least one cedirogant group versus placebo (PASI 75 response rate of 11%) using a two-sided significance level of 0.1 based on the 2-sample Chi-Squared test.

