3.3 Other Efficacy Endpoints

Additional efficacy endpoints include the primary and all secondary endpoints assessed at visits other than the Week 16 Visit as noted in the Study Activities table (Appendix D of the protocol). Additional efficacy endpoints include the following measurements assessed at visits as specified in the Study Activities table:

- Change from baseline in Dermatology Life Quality Index (DLQI) score
- Achievement of a DLQI score of 0 or 1
- Achieving a change of ≥ 4 points from baseline in DLQI score (for patients whose DLQI score at baseline is ≥ 4)
- Treatment Satisfaction Questionnaire for Medication Version 9 (TSQM-9) domain scores (effectiveness, convenience and global satisfaction domains)
- Change from baseline in Hospital Anxiety and Depression Scale (HADS)-Anxiety score
- Change from baseline in HADS-Depression score
- Change from Baseline in Work Productivity and Activity Impairment (WPAI): Psoriasis Questionnaire measures:
 - Percent work time missed (Absenteeism)
 - Percent impairment while working (Presenteeism)
 - Percent overall work impairment
 - Percent activity impairment

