9.2 Handling of Missing Data

Observed Cases (OC) approach will be the only approach to handle missing data for both categorical and continuous efficacy endpoints in the study. The OC analysis will not impute values for missing evaluations, and thus a subject who does not have an evaluation on a scheduled visit will be excluded from the OC analysis for that visit. OC will not include values after a subject prematurely discontinues from study treatment.

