9.5 Additional Efficacy Analyses

Descriptive summary statistics of the additional efficacy endpoints will be provided based on the ITT Population as described in Section 9.1.

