10.3 Analysis of Laboratory Data

Data collected from central and local laboratories, including additional laboratory testing due to an SAE, will be used in all analyses, except for Baseline where SAE-related laboratory assessments on or before the first dose of study drug will be excluded. The clinical laboratory tests defined in the protocol operations manual (e.g., hematology and clinical chemistry) will be summarized.

The raw laboratory variable values and change from baseline to each applicable post-baseline visit will be summarized by treatment group, with number of subjects, mean, standard deviation, median, minimum, maximum. The 95% CI based on normal approximation will be provided for the mean change from baseline.

Laboratory abnormalities meeting CTC criteria grade 3, 4 and ' ≥ 3 ' will be summarized.

Laboratory abnormalities will be evaluated based on Potentially Clinically Important (PCI) criteria ([Appendix C](#)). For each laboratory PCI criterion, the number and percentage of subjects who have a laboratory value meeting the criteria will be summarized. Listings will be provided to summarize subject-level laboratory data for subjects meeting PCI criteria.

Assessment of Liver Enzyme and Bilirubin Elevations

The frequencies and percentages of subjects with post baseline liver specific function test values in ALT/SGPT, AST/SGOT, alkaline phosphatase, and total bilirubin meeting the following criteria will be summarized:

- ALT $> 3 \times$ ULN, $> 5 \times$ ULN, $> 10 \times$ ULN, $> 20 \times$ ULN
- AST $> 3 \times$ ULN, $> 5 \times$ ULN, $> 10 \times$ ULN, $> 20 \times$ ULN
- TBL $> 1.5 \times$ ULN, $> 2 \times$ ULN
- ALT and/or AST $> 3 \times$ ULN and TBL $> 1.5 \times$ ULN
- ALT and/or AST $> 3 \times$ ULN and TBL $> 2 \times$ ULN
- ALT $> 3 \times$ ULN and TBL $> 1.5 \times$ ULN
- ALT $> 3 \times$ ULN and TBL $> 2 \times$ ULN
- Alkaline phosphatase $> 1.5 \times$ ULN

A listing of possible Hy's Law cases, defined as those who meet all of the following conditions simultaneously, will be provided: ALT $> 3 \times$ ULN or AST $> 3 \times$ ULN that is associated with an increase in total bilirubin $\geq 2 \times$ ULN and alkaline phosphatase $< 2 \times$ ULN.

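### SAP 9.1 uses a normal-approximation 95% CI for every responder rate with no sparse-cell rule, so 0/n gets a zero-width interval and 1–3 responders (n ≥ 14) a negative lower limit

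*SAP*

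**What the plan says.** SAP 9.1 sets the rule for all efficacy output: "Descriptive summary statistics will be provided for efficacy endpoints at each visit by treatment groups based on the ITT population". For categorical endpoints the content is the number of subjects, then "the number and percentage of subjects who achieve the endpoint, as well as the 95% confidence interval (CI) based on normal approximation".

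Sections 9.3.2, 9.4.2 and 9.5 send the primary, secondary and additional endpoints back to 9.1. Section 9.5 reads: "Descriptive summary statistics of the additional efficacy endpoints will be provided based on the ITT Population as described in Section 9.1". Section 3.3 widens the scope beyond Week 16: "Additional efficacy endpoints include the primary and all secondary endpoints assessed at visits other than the Week 16 Visit".

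Two other provisions bear on cell size:

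- SAP 2.1: "As the study was terminated prematurely before the planned number of subjects could be randomized", efficacy is summarised descriptively only.
- SAP 9.2, observed cases: "a subject who does not have an evaluation on a scheduled visit will be excluded from the OC analysis for that visit". Values after premature discontinuation of study treatment are also left out.

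The SAP nowhere mentions an exact, score or continuity-corrected interval, truncation at 0% or 100%, or a minimum count. Section 9.6 does not say whether the subgroup tables carry intervals.

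**The concern.** The Wald interval estimates its standard error from the observed proportion. When that proportion is 0 or 1 the standard error is zero, and the interval collapses to a point just where the data say least. Close to 0 or 1 the interval is symmetric where it should be skewed, so it runs past the possible range on one side and stops short on the other.

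Sparse cells can be foreseen here. Placebo PASI 75 is planned at 11% (SAP 2.4), and PASI 90 and PASI 100 rates cannot exceed the PASI 75 rate. The trial stopped short of its planned 200 subjects, and observed-cases denominators vary by visit. With testing dropped and no sensitivity analyses (SAP 9.3.3, 9.4.3), these intervals are the only planned measure of uncertainty for responder rates. What is at stake is the readability and honesty of the descriptive tables, not a trial conclusion.

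**Working it through.** **Inputs.** Placebo PASI 75 rate 11% and planned 50 per arm (SAP 2.4). Implied active rate 11% + 60% = 71%. Actual arm sizes are not in the documents, so cell sizes of 20 to 50 are assumed. Normal approximation is read as Wald.

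**The plan's own figure.** SAP 2.4 claims more than 95% power for 11% against 71%, 50 per arm, two-sided 0.1, chi-squared test. With pooled rate 0.41:

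(0.60 − 1.645 × √(2 × 0.41 × 0.59 / 50)) / √((0.11 × 0.89 + 0.71 × 0.29) / 50) = (0.60 − 0.162) / 0.0779 ≈ 5.6

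Power is therefore above 99.99% and the statement is true. The documents state no figure for the intervals themselves.

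**How many intervals.** The protocol's Study Activities Table schedules PASI and sPGA at six post-baseline visits (Weeks 2, 4, 6, 8, 12, 16). PASI 50/75/90/100 and sPGA clear or almost clear give 5 endpoints × 6 visits × 4 arms = 120 intervals, before the PSS, itch NRS and DLQI responder endpoints. Not all of these will be sparse.

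**When the interval fails.** Wald is p̂ ± 1.96 × √(p̂(1 − p̂)/n), with p̂ = x/n.

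- x = 0 gives 0% to 0%, and x = n gives 100% to 100%, at any n.
- The lower limit is negative when x ≥ 1 and x < 3.84 × (1 − x/n). That holds for x = 1 if n ≥ 2, x = 2 if n ≥ 5, x = 3 if n ≥ 14, and never for x ≥ 4.
- By symmetry, 1 to 3 non-responders push the upper limit above 100% under the same conditions.

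| Responders | Wald | Clopper-Pearson | Wilson |
|---|---|---|---|
| 0/50 | 0 to 0% | 0 to 7.1% | 0 to 7.1% |
| 3/50 | −0.6 to 12.6% | 1.3 to 16.5% | 2.1 to 16.2% |
| 0/25 | 0 to 0% | 0 to 13.7% | 0 to 13.3% |
| 2/25 | −2.6 to 18.6% | 1.0 to 26.0% | 2.2 to 25.0% |

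**How often at 11%.** Zero width has probability P(X = 0) = 0.89ⁿ, a negative limit has P(1 ≤ X ≤ 3), and their total is P(X ≤ 3). Coverage is the sum of binomial probabilities over those x whose interval contains 11%.

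| n | Zero width | Negative limit | Total | Wald coverage |
|---|---|---|---|---|
| 50 | 0.3% | 18.2% | 18.5% | 91.7% |
| 40 | 0.9% | 33.6% | 34.5% | 93.4% |
| 30 | 3.0% | 54.6% | 57.7% | 85.3% |
| 25 | 5.4% | 65.2% | 70.7% | 94.2% |

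Totals are rounded from unrounded values. Over every n from 20 to 50, coverage averages 89.7% and never reaches 95% (lowest 80.7% at n = 27, highest 94.9% at n = 42).

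The misses are lopsided. At n = 50, 0 to 2 responders put the upper limit below 11% (7.6% of samples), and 12 or more put the lower limit above it (0.7%): 100 − 7.6 − 0.7 = 91.7%.

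**At 71%.** Wald averages 93.2% over n = 20 to 50 (88.8% at n = 22 to 95.1% at n = 31), which is close to nominal.

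**At lower rates, assumed and not in the documents.** At 5%, coverage is 92.0% (n = 50) and 72.1% (n = 25). At 2%, it is 63.5% and 39.6%, mostly because 0/n becomes common.

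**The case against.** The strongest reply is that little depends on this. SAP 2.1, 9.1 and 13.0 remove all testing, the interim analysis is cancelled, and the number of subjects, count and percentage stand beside each interval, so a reader can compute a better one. That stands, and it is why the point is minor.

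Second, the more misleading failure, 0/n, is rare at the only low rate in the documents: 0.3% at n = 50 and 5.4% at n = 25. Most of the combined probability is negative limits, which a reader will recognise and take as zero. This also stands. However, placebo PASI 90 and PASI 100 rates can only be equal or lower, and reading a negative limit as zero does not correct the upper limit, which is where most misses occur.

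Third, Wilson also rests on a normal approximation, so the SAP might mean that. It does not say so, and Wald is the usual reading. If Wilson is intended, naming it settles the matter. A continuity-corrected Wald would not: 0/50 would run from −1.0% to 1.0%.

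Finally, Wald is adequate near 71%, so a fallback for sparse cells alone could suffice. That is a fair alternative, though one named interval for all proportions is simpler to specify and to read.

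**Conclusion.** The concern holds, as a minor correction to descriptive output. On the Wald reading, SAP 9.1 yields zero-width intervals for 0/n and n/n, and limits outside 0% to 100% for 1 to 3 responders or non-responders in cells of 14 or more. Even at the full planned 50 per arm and the plan's 11% placebo rate, about one placebo PASI 75 interval in five or six (18.5%) would be of this kind, with 91.7% coverage instead of 95%. The figures for smaller cells depend on assumed sizes and those at 2% and 5% on assumed rates. The algebraic failures depend on neither, only on the Wald reading.

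**What to change.** In SAP 9.1, for categorical endpoints, replace the normal-approximation wording with a named 95% interval, either Clopper-Pearson (exact) or Wilson score. State that the same interval applies to the subgroup proportions in 9.6 if intervals are shown there.

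The cost is one sentence and a procedure option in the existing software. Each choice has a small downside over n = 20 to 50:

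| Interval | Coverage at 11% | Coverage at 71% |
|---|---|---|
| Clopper-Pearson | 95.5 to 99.3% | 95.1 to 98.4% |
| Wilson | 92.0 to 97.8% | 92.8 to 96.5% |

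Clopper-Pearson is therefore somewhat wide, and Wilson can dip a little below nominal.

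An optional tidy-up concerns mean change from baseline, where 9.1, 10.3 and 10.4 also specify a normal approximation (in 10.3: "The 95% CI based on normal approximation will be provided for the mean change from baseline"). A t-based interval would be cleaner, but for normally distributed changes the z interval still covers 94.4% at n = 50 and 93.5% at n = 20, so nothing of substance turns on it.

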2.3 Treatment Assignment and Blinding

All subjects will be assigned a unique identification number by the IRT at the screening visit. For subjects who rescreen, the screening number assigned by the IRT at the initial screening visit should be used. The IRT will assign a randomization number that will encode the subject's treatment group assignment according to the randomization schedule.

Subjects who meet eligibility criteria at Baseline will be randomized in a 1:1:1:1 ratio to 1 of the 4 treatment groups:

- Cedirogant 375 mg once daily (QD) (N = 50)
- Cedirogant 150 mg QD (N = 50)
- Cedirogant 75 mg QD (N = 50)

- Placebo QD (N = 50)

All active and placebo treatment will be taken orally (cedirogant 75 mg tablets and matching placebo). There is no stratification factor for the randomization.

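### The 95% CIs for mean change from baseline rest on the normal approximation although the SD is estimated: coverage is slightly below 95%, and visibly so only if cells are small

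*SAP*

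**What the plan says.** SAP 9.1, on continuous efficacy endpoints: "The 95% CI based on normal approximation will be provided for the mean change from baseline". SAP 10.3 repeats the sentence for laboratory variables and SAP 10.4 for systolic and diastolic blood pressure. These are the only places where the SAP plans an interval for a mean change. Each also reports the number of subjects, the mean and the SD. The SAP gives no formula or multiplier, does not mention the t distribution, and has no rule for small samples.

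The efficacy measures affected are the changes in DLQI, the two HADS scores and the WPAI measures (SAP 3.3). The primary endpoint and all six secondary endpoints are binary (SAP 3.1 and 3.2). Their intervals for proportions are a separate provision of SAP 9.1 and are not part of this point.

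On cell size, SAP 2.4 begins "Given the planned total sample size of 200 subjects (50 subjects in each arm", and SAP 2.3 has subjects "randomized in a 1:1:1:1 ratio to 1 of the 4 treatment groups". SAP 2.1 then records that "the study was terminated prematurely before the planned number of subjects could be randomized". For efficacy endpoints SAP 9.2 uses Observed Cases only and adds that "OC will not include values after a subject prematurely discontinues from study treatment". For safety, SAP 10.1 says only that missing data are not imputed. Neither document gives the number randomized or the number evaluable at any visit.

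On use, SAP 2.1, 9.1 and 13.0 say that no statistical comparison or test will be made.

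**The concern.** The normal quantile is the right multiplier when the SD is known, or when n is large enough that estimating it hardly matters. Here the SD is estimated within each arm and visit. An interval built as mean ± 1.96 × SD/√n is then too short, and its true coverage is below the 95% on its label.

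This SAP has no tests and no sensitivity analyses of the primary or secondary endpoints, and its version history records that Observed Cases replaced the mixed model for continuous endpoints. For mean changes, these intervals are the only planned statement of uncertainty about the mean. The same rule covers laboratory and blood pressure changes in a trial that was stopped because of preclinical findings. What is at stake is the accuracy of a label on descriptive tables, not a conclusion about efficacy.

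**Working it through.** **The plan's own figure.** The documents state no coverage for these intervals. The only design figure is in SAP 2.4: "the study has more than 95% power to detect the treatment differences of 60% in PASI 75", against a placebo rate of 11%, "using a two-sided significance level of 0.1 based on the 2-sample Chi-Squared test". With 50 per arm and rates of 0.11 and 0.71, the pooled rate is 0.41.

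- SE under the null: √(2 × 0.41 × 0.59 / 50) = 0.0984
- SE under the alternative: √((0.11 × 0.89 + 0.71 × 0.29) / 50) = 0.0779
- Power: Φ((0.60 − 1.645 × 0.0984) / 0.0779) = Φ(5.62), which exceeds 0.9999

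The stated power therefore holds. It concerns a binary endpoint and says nothing about intervals for means. It is used here only for the planned arm size of 50.

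**Inputs for the interval.**

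- Nominal level 95% and normal approximation, from SAP 9.1, 10.3 and 10.4. Read literally, the multiplier is 1.960.
- SD estimated from the n subjects in the cell.
- n unknown. The range 5 to 50 is an assumption, with the planned arm size at the top.

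**Formulas, for normally distributed changes.**

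- Coverage of the planned interval: P(|t(n−1)| < 1.960) = 2 × F(1.960; n−1) − 1, where F is the t distribution function.
- Widening needed for 95% coverage: t(0.975, n−1) / 1.960.

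At n=20, for example, t(0.975, 19) = 2.093. Coverage is 93.5% and the widening is 2.093/1.960 = 1.068, or 7%.

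| n | t multiplier | Coverage of planned interval | t interval wider by |
|---|---|---|---|
| 5 | 2.776 | 87.8% | 42% |
| 10 | 2.262 | 91.8% | 15% |
| 15 | 2.145 | 93.0% | 9% |
| 20 | 2.093 | 93.5% | 7% |
| 30 | 2.045 | 94.0% | 4% |
| 50 | 2.010 | 94.4% | 2.5% |

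Simulation with 200,000 normal samples at n = 5, 10, 20, 30 and 50 agrees with these coverages to within 0.1 percentage point. Coverage first reaches 94% at n=30. It reaches 94.5% only at n=57, above the planned arm size.

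**Sensitivity to the normal assumption.** With strongly skewed (exponential) data, simulated coverage is:

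| n | Normal approximation | t interval |
|---|---|---|
| 10 | 86.9% | 90.0% |
| 20 | 90.5% | 91.9% |
| 50 | 92.9% | 93.5% |

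The t interval is better at each n, but stays below 95%.

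**The case against.** The case for leaving the text alone is reasonable. The intervals are within-arm and descriptive. They cover additional efficacy measures (by Protocol Appendix D, HADS and WPAI are scheduled at two post-baseline weeks and DLQI at three), laboratory values and blood pressure. Since n, mean and SD are tabulated, any reader can rebuild the t limits. At n of 30 or more the difference is hardly noticeable. The SAP prints no formula, so the programs may already use t limits, in which case only the wording is wrong. All of this stands. It limits the size of the point but does not make the stated rule correct.

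A reader might also infer more than the documents support:

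- **That cells are known to be small after termination.** The documents say only that enrolment fell short of plan. The figures at n=5 and n=10 illustrate a possibility; they are not findings about this trial.
- **That Observed Cases also shrinks the safety cells.** SAP 9.2 applies that approach to efficacy endpoints. No exclusion of values after treatment discontinuation is stated for laboratory or vital-sign data.
- **That the rule was carried over unrevised when the trial stopped.** SAP version 1.0 is not available, so this cannot be checked.
- **That the t interval is a complete repair.** It is exact only for normal changes, which is not assured for questionnaire scores and percentages in small cells.

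**Conclusion.** The point holds, as a minor one. As worded, SAP 9.1, 10.3 and 10.4 give intervals for the mean change that are too narrow for their label. The direction does not depend on the unknown n: for normal changes, coverage is below 95% at every cell size up to the planned 50 per arm. The size does depend on n. The shortfall is 0.6 percentage points at n=50, 1.0 at n=30, 1.5 at n=20 and 3.2 at n=10 (95% minus the tabulated coverage). It is visible in a table only if cells fall to about 20 or fewer.

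This rests on two assumptions: that the normal approximation means a multiplier of 1.96, and that changes are roughly normal. No test, comparison or primary or secondary result is affected.

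**What to change.** In SAP 9.1 (the sentence on mean change for continuous endpoints), 10.3 and 10.4, state that the 95% CI for the mean change is based on the t distribution with n−1 degrees of freedom, in place of the normal approximation. If the programs already compute t limits, the same edit brings the text into line with them.

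The cost is a wording change in three places. It needs no new data or tables, because the limits use the n, mean and SD already planned. The intervals widen by the percentages in the table above. The change does not repair the intervals for proportions in SAP 9.1, which need their own treatment. For strongly skewed variables in small cells, the intervals should still be read with caution.
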